- Viral Load, CD4/CD8 count (HIV infected Subjects);
- Perform PK blood sample (at 9AM \pm 1hour);
- Adverse event assessment.

5.3.8. End of Study Visit (D56 for cohort 1&2 or D112 for cohort 3; \pm 7 days)

- Physical examination and vital signs;
- Microbiome specimen collection (swabs);
- Hematology (incl. INR and PT if clinically indicated);
- Biochemistry;
- Urine GC/CT NAAT & Rectal GC/CT NAAT;
- HIV serology (HIV uninfected participants)
- 12 lead ECG;
- Viral Load, CD4/CD8 count (HIV infected Subjects);
- Blood collection for HIV reservoir assessment (HIV infected Subjects) and immuno-evaluation;
- Flexible sigmoidoscopy with collection of rectal biopsies (Cohort 1 and 3 only)
- Perform PK blood sample (at 9AM \pm 1hour);
- Adverse event assessment.

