8.4. Time Period, and Frequency of Detecting AEs and SAEs

All AEs and SAEs occurring from the time a subject consents to participate in the study until 4 weeks after he or she has completed or discontinued the investigational product must be recorded in the subject's eCRF. Importantly, SAEs will have to be reported to ABIVAX or its designee within 24 hours of awareness of an SAE.

Legislative guidance requires also reporting any **related** SAEs to be reported after the subject finished the study if the investigator becomes aware of them.

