### 3.4 Study Timepoints

From a subject standpoint, the study participation is defined as

- Two to four weeks of screening period;
- Four weeks (Cohorts 1 & 2) or twelve weeks (Cohort 3) as the treatment period (ABX464);
- Follow-up visits at 1 week and 4 weeks after cessation of study medication.

Overall, the minimal study duration is approximately 70 days and up to 140 days depending on the subject Cohort.

Visits and visit windows are defined as follows:

Visit	Study Day	Window
-------	-----------	--------

Screening	-21	± 7 days
Baseline	1	
Control (Cohort 2 only)	7	± 2 days
Control (Cohort 2 only)	14	± 2 days
Control (Cohort 2 only)	21	± 2 days
Day 28 (Cohort 3 only)	28	± 2 days
End of Study Treatment (Cohort 1 & 2)	28	± 2 days
Follow-up (Cohort 1 & 2)	35	± 2 days
End of Study (Cohort 1 & 2)	56	± 7 days
Day 56 (Cohort 3 only)	56	± 2 days
End of Study Treatment (Cohort 3 only)	84	± 2 days
Follow-up (Cohort 3 only)	91	± 2 days
End of Study (Cohort 3 only)	112	± 7 days

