## 10.2 Missing Data

There will be no imputation of missing data in this study.

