### 11.4.1 Adverse Events

All adverse events (AE) will be classified using the version of the MedDRA coding dictionary.

Events will be classified as treatment-emergent if they started or increased in severity on or after the first date and time of medication dosing at Day 1 and up to End of Rx, or withdrawal date if the

patient discontinues before End of Rx. If an event start date is partial, then the start day, month, year or stop date will be used to determine if the event is treatment-emergent. If the classification of the AE cannot be determined from the data available, then the event will be considered treatment-emergent.

Any adverse event which occurs after End of Rx will be classified as post-treatment-emergent.

An overall summary table will be presented using the safety set for adverse events occurring from baseline to the end of the study in the following categories:

- Any adverse event;
- Any treatment-emergent adverse event (TEAE);
- Any post-treatment-emergent adverse event;
- Any serious adverse event;
- Any severe adverse event (Common Toxicity Criteria [CTC] grade 3 or 4);
- Death

TEAEs will be further classified and summarised as follows:

**Severe TEAEs:** Severity classified as 'Grade 3', 'Grade 4' or missing.

**Serious TEAEs:** Seriousness classified as 'yes' or missing.

**Drug-related TEAEs:** Relationship to study drug classified as 'yes' or missing.

**Serious drug-related TEAEs:** Both serious and drug-related, as specified above.

**TEAEs leading to study drug discontinuation:** Action taken classified as 'permanent discontinuation'.

Summaries by system organ class (SOC) and preferred term (PT) will also be presented for treatment-emergent events. Similar tables will be presented for each of the classifications of treatment-emergent events above.

A summary of the mean duration (days) of treatment-emergent events will also be presented by SOC and PT, along with the number of events. Duration of an event is calculated as (stop date of event - start date of event) + 1. If an AE is ongoing then use the end of study date (or last known visit date for early termination) as the stop date.

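### The adverse-event duration table scores events still ongoing at end of study as finished, which understates mean duration for long events, and more so in Cohorts 1 and 2 than in Cohort 3

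*SAP*

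**What the plan says.** SAP 11.4.1 (Adverse Events) specifies this table: "A summary of the mean duration (days) of treatment-emergent events will also be presented by SOC and PT, along with the number of events". The derivation is "Duration of an event is calculated as (stop date of event - start date of event) + 1", and for events without an end: "If an AE is ongoing then use the end of study date (or last known visit date for early termination) as the stop date". No count of ongoing events and no censored summary is specified for the table. SAP 10.1 puts the three cohorts in adjacent columns.

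An event is treatment-emergent if it starts or worsens "on or after the first date and time of medication dosing at Day 1 and up to End of Rx". SAP 3.4 sets the treatment period at four weeks for Cohorts 1 and 2 and twelve weeks for Cohort 3. Protocol 5.3.8 places the "End of Study Visit (D56 for cohort 1&2 or D112 for cohort 3", with a window of 7 days either side. Protocol 8.4 has events recorded "until 4 weeks after he or she has completed or discontinued the investigational product must be recorded in the subject's eCRF", so follow-up after treatment is the same length in every cohort. After premature discontinuation, Protocol 7.3 asks for the End of Study visit within two weeks of the last dose.

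SAP 10.2 states: "There will be no imputation of missing data in this study". Protocol 8.5 records start date, stop date and outcome for each event, and the outcome categories include an ongoing one.

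**The concern.** An event still open at end of study is right-censored: its true duration is at least the assigned one. Treating that minimum as a completed duration pulls the mean down. The pull is strongest for the persistent events that a duration table ought to reveal. The amount depends on how long an event could be watched, and that differs by cohort when averaged over the treatment period. Part of a difference between the Cohort 1 and Cohort 3 columns could then come from length of follow-up alone. With only a mean and an event count in the table, a reader cannot tell how many of the averaged values are minimum values.

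**Working it through.** **Check of the follow-up schedule.** SAP 3.4 gives participation of about 70 to 140 days. Shortest: 14 + 28 + 28 = 70. Longest: 28 + 84 + 28 = 140. Both agree with the plan.

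**Direction, without any assumption.** With true duration D and cap c, the table uses min(D, c), which never exceeds D. The mean is therefore at or below the truth, and below it whenever an event outlasts its cap.

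**Longest duration that can be scored.** Cap = End of Study day − onset day + 1.
- Cohorts 1 and 2, onset Days 1 to 28: from 56 − 1 + 1 = 56 down to 56 − 28 + 1 = 29 days; average (56 + 29)/2 = 42.5.
- Cohort 3, onset Days 1 to 84: from 112 − 1 + 1 = 112 down to 112 − 84 + 1 = 29 days; average (112 + 29)/2 = 70.5.
- Same study-day onset: the Cohort 3 cap is 112 − 56 = 56 days longer.
- Same distance from End of Rx: equal caps. Onset on the last dosing day gives 29 days in every cohort; onset 7 days earlier gives 36 days in every cohort.
- Premature discontinuation (illustration): onset Day 7, last dose Day 14 and End of Study by Day 28 give at most 28 − 7 + 1 = 22 days. A completer with the same onset could reach 50 days in Cohorts 1 and 2, or 106 in Cohort 3.

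**Size.** The documents give no event durations, so two assumptions are needed: D is exponential with mean m, the same in all cohorts, and onset is uniform over the treatment days. Then, averaging over the caps c,

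- expected tabulated mean = average of m × (1 − exp(−c/m));
- share ongoing = average of exp(−c/m), which under this model equals the proportional understatement.

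Example, m = 30. Cohorts 1 and 2: exp(−c/30) summed over c = 29 to 56 is 7.04; 7.04/28 = 0.251; 30 × 0.749 = 22.5 days. Cohort 3: the sum over c = 29 to 112 is 10.90; 10.90/84 = 0.130; 30 × 0.870 = 26.1 days.

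| True mean (days) | Cohorts 1 and 2: tabulated mean (ongoing) | Cohort 3: tabulated mean (ongoing) | Ratio |
|---|---|---|---|
| 7 | 7.0 (0%) | 7.0 (0%) | 1.00 |
| 14 | 13.2 (6%) | 13.7 (2%) | 1.04 |
| 30 | 22.5 (25%) | 26.1 (13%) | 1.16 |
| 60 | 30.2 (50%) | 39.9 (33%) | 1.32 |
| never resolves | 42.5 (100%) | 70.5 (100%) | 1.66 |

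With onset in continuous time rather than whole days, the 30-day row becomes 22.3 vs 26.0 and the 60-day row 29.9 vs 39.8 (ratio 1.33).

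**Do the alternatives work?** Simulation of 400,000 events per setting under the same assumptions:
- Kaplan-Meier median with ongoing events censored: 19.4 days under both schedules for a true mean of 28 days (true median 19.4); 38.7 under both for a true mean of 56 days (true median 38.8).
- Mean of resolved events only: 16.1 vs 21.3 days (true mean 28) and 18.9 vs 28.7 (true mean 56). Dropping ongoing events is therefore no remedy.

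These are large-sample results. They show absence of bias, not precision with 12 subjects per cohort.

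**The case against.** The strongest case against the point is that it has little consequence. This is one supplementary table with no test or decision attached. The adverse-event endpoint in SAP 4.2 is number and grade, not duration. Cohorts 1 and 3 differ in dose and treatment length, and Cohort 2 also differs from both in HIV status, without randomisation, so a contrast in durations is confounded whatever the rule. Adverse events are listed individually and the ongoing outcome is collected, so the information is not lost. All of this stands and limits the importance of the point; it does not make the tabulated mean correct.

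Three stronger readings are tempting and are not supported:

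- **That any given event looks longer in Cohort 3.** An event that resolves before the cut-off has the same duration in every cohort. Events starting equally close to End of Rx also share the same cap. The gap needs unresolved events, compared at the same study-day onset or averaged over treatment.
- **That the bias must be substantial.** Nothing in the documents implies means of 30 days or more. For events of about a week the effect is nil.
- **That the rule breaches the no-imputation statement in SAP 10.2.** That sentence concerns missing data, whereas SAP 11.4.1 sets an explicit convention for one derived variable, alongside others for partial dates and missing severity, seriousness and relationship. At most the wording of 10.2 could be tidied.

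It can also fairly be said that Kaplan-Meier estimates for every preferred term would be out of proportion with 12 subjects per cohort. That is accepted in the fix.

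**Conclusion.** The point holds for events unresolved at end of study, and is minor. The downward direction follows from the rule itself. So does the 56-day difference in cap for the same study-day onset, at the scheduled visit days. The size rests on assumed exponential durations, uniform onset and full follow-up to the scheduled visit. For true means from 7 to 60 days, understatement runs from 0% to about 50% and the spurious excess in Cohort 3 from 0% to about 33%. Those are the ends of an assumed range, not bounds; longer-lasting events would be affected more. No primary result, named endpoint or error rate is touched.

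**What to change.** In SAP 11.4.1, stop treating ongoing events as completed in the duration table:

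- For each SOC and PT and each cohort, give the number of events ongoing at end of study beside the number of events, and flag their durations as censored (minimum) values. This is the core change.
- Where event counts allow, for example overall or by SOC, give a Kaplan-Meier median time to resolution with ongoing events censored at the date the SAP now uses as their stop date.
- For sparse terms, list the durations with an ongoing flag instead of a mean.

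Optionally, add to SAP 10.2 that conventions for derived adverse-event variables are set in 11.4.1.

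The cost is a few lines of SAP text, a revised table shell and one standard SAS procedure; no new data are needed. The drawbacks are that the median may not be reached for sparse terms, and that repeat events within a subject are not independent, so the estimates should be read as descriptive only.

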#### 11.4.2 Laboratory Data

Routine clinical laboratory results will be carried out at screening, all visits during the treatment period. The laboratory parameters include:

- Haematology: hemoglobin, hematocrit, WBC, neutrophils, lymphocytes, monocytes, eosinophils, basophils, platelet count, INR, PT
- Biochemistry: sodium, potassium, chloride, calcium, phosphate, glucose, BUN or urea, creatinine, AST, ALT, alkaline phosphatase, total bilirubin, GLDH, total protein, lipase, albumin, LDH, gGT, CRP,

Laboratory parameters will be summarised at each visit using descriptive statistics on the SAF set. Laboratory parameters classified as normal/ abnormal non clinically significant (NCS)/ abnormal clinically significant (CS) will be presented in a shift table showing changes from baseline to each visit for patients with at least one abnormal CS value. Baseline is defined as the last non-missing value before the first dose of study drug, which is Day 0.

If laboratory results are repeated at the same visit, the repeated result will be used in summaries (instead of the original one) provided the sample was taken within the visit window, otherwise the original result will be used. All results will be listed.

Laboratory results at unscheduled visits will be included in the listings but will not be summarised.

For all female patients of childbearing potential, a blood pregnancy test ( $\beta$ -HCG) will be performed at Day 0 and then a urine pregnancy test will be performed at each visit until VR. Results of all pregnancy testing will be listed only.

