9.3.1. Clinical laboratory evaluation

Descriptive statistics for laboratory parameters will be computed at each scheduled assessment. If relevant for some parameter, change from baseline will also be tabulated.

In addition, shift tables from baseline will be presented.

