#### 4.4 Safety endpoint

Analysis of safety will be performed on the safety data set consisting in all subjects who received at least one dose of ABX464 in the study. The assessment of safety will be based on the frequency of adverse events (with and without regard to causality) graded according to the Division of AIDS table for grading the severity of adult and pediatric adverse events (Version 2.0 November 2014) and also, the review of individual values for clinical laboratory data, vital signs and ECG focusing on the detection of abnormal values and PCSAs [potentially clinically significant abnormalities (PCSA) determined upon investigator considerations].

Adverse events will be tabulated (counts and percents) by group and dose. All adverse events will be listed and the data will be tabulated by body system/organ class. Adverse event tabulations will include all treatment emergent adverse events, which will be further classified by severity, and relationship to treatment and dose level.

Clinical laboratory parameters, vital signs, ECG will be summarized by using descriptive statistics (n, mean, SD, SEM, median, minimum and maximum). Number of subjects with at least one abnormal values will be tabulated (counts and percents) for each parameter in summary shift tables, by group and dose.

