# 11 Statistical Output

General principles for layout of the statistical output are described in Section 10.1, including specification of the table columns, and these are illustrated for each unique table in the table shells (separate document). For clarity and brevity in this document the phrase “by treatment group” or “by study cohort” is understood for all summaries and is not included within the text of this section.

The study analysis will be performed following database lock upon the completion of the last patient or upon its early discontinuation whichever occurs first.

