#### 11.4.5 Electrocardiogram

A 12-lead ECG will be completed at Screening, Day 0, End of Rx, and End of Study visit.

The number and percentage of the patients with Normal / Abnormal NCS / Abnormal CS ECG results will be summarised at each visit.

A shift table will be presented, for patients with at least one Abnormal CS value, showing changes from baseline to each visit. Baseline is defined as the last non-missing value before the first dose of study drug, which is Day 0.

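### The SAP's laboratory shift table admits only patients with a clinically significant value, so it does not deliver the promised count of subjects with any abnormal value

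*SAP*

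**What the plan says.** SAP 4.4 covers laboratory parameters, vital signs and ECG together and states: "Number of subjects with at least one abnormal values will be tabulated (counts and percents) for each parameter in summary shift tables". These tables are to be split by treatment group and dose level. The same sentence stands in the protocol synopsis and in protocol 9.3. For laboratory data, protocol 9.3.1 adds: "In addition, shift tables from baseline will be presented". None of these places limits the table to a subgroup.

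SAP 11.4.2 is the only place that specifies the laboratory shift table. Results classified as normal, NCS or CS "will be presented in a shift table showing changes from baseline to each visit for patients with at least one abnormal CS value". The other laboratory outputs there are descriptive statistics by visit on the safety set and listings of all results. On what enters the summaries it says: "Laboratory results at unscheduled visits will be included in the listings but will not be summarised". A repeat replaces the first result "provided the sample was taken within the visit window, otherwise the original result will be used".

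The ECG section, SAP 11.4.5, has the same CS-only shift table but sets an unrestricted summary beside it: "The number and percentage of the patients with Normal / Abnormal NCS / Abnormal CS ECG results will be summarised at each visit". The laboratory section has no such sentence. SAP 11.4.3 gives vital signs descriptive statistics only.

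**The concern.** Two live parts of the SAP disagree, and the more detailed one also departs from the protocol. The promise puts the abnormal-value count inside the shift table. The detailed specification then builds a shift table that excludes some of the subjects who belong in that count. A programmer working from 11.4.2 would not produce the promised number.

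Safety is a secondary objective, and abnormal laboratory values are one of its stated measures. Whether a value is CS is the investigator's judgement (protocol 5.4.3), made in an open-label study. The restriction therefore replaces a count based on reference ranges with a table whose membership depends on that judgement. NCS abnormalities are plausible here: protocol 4.2.1 admits subjects with liver enzymes, bilirubin, creatinine or lipase somewhat above the upper limit of normal.

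**Working it through.** The plan gives no figure to reproduce. The check is a comparison of text, followed by simple arithmetic on size.

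**1. The places side by side**

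| Place | Who is in the shift table | Count of subjects with any abnormal value |
|---|---|---|
| Synopsis, protocol 9.3, SAP 4.4 | no restriction | promised: n and %, per parameter |
| Protocol 9.3.1 (laboratory) | no restriction | not mentioned |
| SAP 11.4.2 (laboratory) | only patients with a CS value | none |
| SAP 11.4.3 (vital signs) | no shift table | none |
| SAP 11.4.5 (ECG) | only patients with a CS value | n (%) Normal/NCS/CS at each visit, unrestricted |

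**2. Abnormal does not mean CS.** SAP 11.4.2 itself has two abnormal categories. SAP 4.4 also keeps abnormal values apart from potentially clinically significant abnormalities (PCSAs): safety rests partly on "the review of individual values for clinical laboratory data, vital signs and ECG focusing on the detection of abnormal values and PCSAs". The promised count therefore covers NCS and CS together.

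**3. Who is left out.** For one parameter and cohort, let k be the number of subjects whose abnormal values in that parameter are all NCS, and let m of these have a CS value in some other parameter. SAP 11.4.2 does not say whether the CS value must be in the same parameter.
- Same parameter required: k subjects are left out.
- Any parameter suffices: k − m are left out, which lies between 0 and k.

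The table gives the promised count only if the number left out is zero.

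**4. Size per subject.** The documents do not give k. One subject is 1/12 = 8.3 percentage points of a cohort of 12, and 1/36 = 2.8 points of all 36. Withdrawn subjects are replaced (protocol 6.4 and 7.2) while everyone dosed stays in the safety set, so the denominator can exceed 12. With one replacement it is 1/13 = 7.7 points.

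**5. Number of counts.** SAP 11.4.2 names 11 haematology and 19 biochemistry parameters: 11 + 19 = 30, or 30 × 3 = 90 counts over three cohorts. The visit lists in protocol 5.3 ask for INR and PT after screening only if clinically indicated, although protocol 5.4.3 says every visit. On the visit-list reading, 28 parameters are routine, giving 28 × 3 = 84 counts. These figures describe the tabulation promised, not the loss.

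**6. Comparability of the restored count.** Scheduled post-baseline laboratory visits in protocol 5.3 number 3 in Cohort 1 (Days 28, 35, 56) and 5 in Cohort 3 (Days 28, 56, 84, 91, 112). For an assumed chance p of an abnormal value per draw, independent between draws, the chance of at least one is 1 − (1 − p)^n:

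| p (assumed) | n = 3 | n = 5 |
|---|---|---|
| 2% | 1 − 0.98³ = 5.9% | 1 − 0.98⁵ = 9.6% |
| 5% | 1 − 0.95³ = 14.3% | 1 − 0.95⁵ = 22.6% |
| 10% | 1 − 0.90³ = 27.1% | 1 − 0.90⁵ = 41.0% |

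Abnormal values tend to persist within a subject, so independence overstates the gap. The direction still matters when cohorts are compared.

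**The case against.** The best defence is that the count is not missing from the SAP. SAP 4.4 is current text, 11.4.2 does not withdraw it, and SAP 11.4 introduces its outputs as additional to the analysis of the secondary safety endpoint. This stands in part: it is wrong to say that the SAP never promises the count. However, the safety item among the secondary endpoints in SAP 4.2, analysed in 11.3.2.1, is adverse events. No part of SAP section 11 says how the laboratory count would be produced.

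Second, SAP 11 refers to table shells in a separate document. They may contain the count. This stands as a limit: the mismatch in wording is certain, but its effect on the output is not.

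Third, little may be lost. All results are listed, by-visit minimum and maximum show extreme scheduled values, and CS findings are recorded as adverse events under protocol 8.3.1. The study is descriptive, and no stated decision rule uses the count. This lowers the severity, but none of these outputs gives the number of subjects with an abnormal value.

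A reader might also infer that abnormal results are hidden, or that the rules on unscheduled and repeat results break the promise. The documents support neither reading. The listings keep every result, and those rules can lower a count without contradicting the sentence that promises it.

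**Conclusion.** The conflict is real. SAP 11.4.2, as the only detailed specification, implements something narrower than SAP 4.4, protocol 9.3, protocol 9.3.1 and the synopsis state. Subjects with only NCS abnormalities drop out of the shift table, wholly or in part depending on how the CS condition is read, and no other output in 11.4.2 counts them. Vital signs share the gap: SAP 4.4 covers them, and 11.4.3 gives no abnormal count.

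The size of the loss cannot be stated, because the number of such subjects is unknown; each is about 8 points of a cohort of 12. The conclusion assumes that the shells follow the SAP text. It is a minor to moderate reporting issue: a promised safety statistic would not be produced as written, but the underlying data remain available.

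**What to change.** In SAP 11.4.2:
- Present the laboratory shift table for all safety-set subjects.
- Add, per parameter and cohort, the n (%) with at least one post-baseline abnormal value (NCS or CS). Use the number of subjects assessed as denominator, which matters most for INR and PT. Keep the existing rule on unscheduled results. Copying the ECG sentence alone would not be enough, because it counts by visit and not subjects over all visits.

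Elsewhere:
- State one repeat rule in SAP 10.1 and 11.4.2. For a repeat taken outside the visit window, 10.1 uses the repeat and 11.4.2 the first result.
- Supply the same abnormal-value count for vital signs in SAP 11.4.3.
- Bring the table shells into line.
- Note that scheduled draws differ by cohort, so between-cohort differences need care. Day 28 is the on-treatment visit after Day 1 that all three cohorts share, so its column in the unrestricted table gives the closest comparison.

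If the sponsor prefers the restricted table, SAP 4.4 should be amended and the departure from protocol 9.3 and 9.3.1 justified.

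The cost is SAP wording and a little more tabulation. Protocol 5.4.3 already requires laboratory results and reference ranges in the eCRF, so no new laboratory data are needed.
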